4.2.3. SHORT FORM 36-ITEM HEALTH SURVEY, VERSION 2 (SF-36v2)

The scoring for SF-36 v2 instrument will be done according to the procedures described by the developer and license owner in the instruction manual. Scores for the scales (HT, GH, PF, RP, BP, MH, SF, RE, VT) as well as the summary scores (PCS, MCS) will be derived.

Given SF-36 is collected at Week 23 and at Week 24, an assessment will be derived as the mean value of the two assessments at Week 23 and Week 24, which will be labeled as Week 24. In case only one assessment is available, this only assessment will be used as Week 24 assessment.

Document: \\ieedc-vnasc01\Sites\ [REDACTED]\NLHOF\IntProjects\Consulting\Projects\ Corvidia\ [REDACTED]
Biostatistics\01.Documentation\02.SAPI Corvidia_RESCUE_PROSAP_v2.0_21JUL2020
Author: [REDACTED] Version No: v.2.0
Template No.: [REDACTED] Version Date: 21JUL2020
Effective Date: 01Dec2018 Reference: [REDACTED]

Change from baseline defined as post-baseline value minus baseline value will be calculated for each assessment. At each post-baseline assessment, the change in score from baseline will be calculated for each scale.

4.2.4. EQ-5D-5L

A unique EQ-5D-5L health state is defined by combining 1 level from each of the 5 dimensions: this defines a profile that is primarily reported as a 5-digit number, for instance 11221. A total of 3125 possible health states are defined in this way. For example, state 11111 indicates no problems on any of the 5 dimensions, while state 12345 indicates no problems with mobility, slight problems with washing or dressing, moderate problems with doing usual activities, severe pain or discomfort, and extreme anxiety or depression.

The instrument was specifically designed to provide an overall single number, called a weighted index, for each of the health states resulting from the combination of item responses (Dolan, 1997). The weighted index constitutes a measure of utility, an economics term used to describe consumer preferences or in the present case patient preferences for different HRQoL states. The weighted index can be only derived from patients who have provided a complete 5-response profile. A higher index indicates better QoL.

(Devlin, 2018) published the value set for England (available on the EuroQoL website (<http://www.euroqol.org/about-EQ-5D/valuation-of-EQ-5D/EQ-5D-5L-value-sets.html>)). However, in August 2018, the UK's National Institute of Health and Care Excellence (NICE) has published a position statement (NICE position statement, available at https://www.nice.org.uk/Media/Default/About/what-we-do/NICE-guidance/NICE-technology-appraisal-guidance/eq5d5l_nice_position_statement.pdf) advising companies, academic groups, and others preparing evidence submissions to NICE not to use the England validation set to derive utility values for their evidence submissions. In their position statement, NICE recommends using the mapping function developed by (van Hout & al., 2012) to be used (presented in Appendix D. EQ-5D-5L). This is the algorithm to be used in this study.

Change from baseline defined as post-baseline value minus baseline value will be calculated for each assessment for the EQ-5D-5L VAS and utility index scores as well as for the individual domain items.

4.2.5. PATIENT GLOBAL IMPRESSION OF SEVERITY (PGIS) AND CHANGE (PGIC)

The PGIS and PGIC are single-item questionnaires. Change from baseline defined as post-baseline value minus baseline value will be calculated for the PGIS assessment. At each post-baseline assessment, the change from baseline will be calculated.

Post-baseline PGIS raw scores will be classified according to the following item response categories:

- Worsening 3 points compared to baseline
- Worsening 2 points compared to baseline
- Worsening 1 point compared to baseline

Document: \\ieedc-vnasc01\Sites\ [REDACTED]\NLHOF\IntProjects\Consulting\Projects\ Corvidia\ [REDACTED]\Biostatistics\01.Documentation\02.SAPI Corvidia_RESCUE_PROSAP_v2.0_21JUL2020
Author: [REDACTED] Version No: v.2.0
Template No.: [REDACTED] Version Date: 21JUL2020
Effective Date: 01Dec2018 Reference: [REDACTED]

Copyright © 2018 [REDACTED] All rights reserved. The contents of this document are confidential and proprietary to [REDACTED] and its subsidiaries. Unauthorized use, disclosure or reproduction is strictly prohibited.

- Stable
- Improved 1 point compared to baseline
- Improved 2 points compared to baseline
- Improved 3 points compared to baseline.

4.3. TIME TO PRO DETERIORATION

Time to clinically meaningful symptom worsening or HRQoL deterioration (PRO deterioration) will be analysed separately for each scale of the PRO instruments collected in this study, as appropriate and as described in Section 5. For convenience, a generic term "time to clinically meaningful deterioration" will be used both for symptom worsening and HRQoL deterioration, with an understanding of a specific meaning depending on the scale or subscale analysed. Two definitions will be used and described in the following sections:

- Time to first deterioration (TTFD)
- Time to definitive deterioration (TTDD)

4.3.1. TIME TO FIRST CLINICALLY MEANINGFUL DETERIORATION (TTFD)

TTFD will be defined as the duration of time from the date of randomization to the date of the first deterioration in PRO scores of at least one threshold-point (see section 4.2 for the definition of deterioration) as compared to the baseline score.

For those patients who experienced a first clinically meaningful deterioration, TTFD will be computed as follows and then converted to months:

TTFD = Date of assessment when first clinically meaningful deterioration of at least one threshold unit was observed – Date of randomization + 1

Patients who did not experience clinically meaningful deterioration will be censored at the date of the last available PRO assessment (i.e., date of the last non-missing value). Patients with no baseline assessment or patients with no post-baseline assessments will be censored at the date of randomization.

4.3.2. TIME TO DEFINITIVE CLINICALLY MEANINGFUL DETERIORATION (TTDD)

TTDD will be defined as the duration of time from the date of randomization to the date of the first deterioration in PRO scores of at least one threshold-point (see section 4.2 for the definition of deterioration) as compared to the baseline score if the deterioration is also observed at all time points thereafter (e.g., after the first deterioration is observed) or if the patient dropped out after deterioration, resulting in missing data.

For those patients who experienced a definitive meaningful deterioration, TTCD will be computed as follows and then converted to months:

TTCD = Date of assessment when first definitive clinically meaningful deterioration was observed – Date of randomization + 1

Document: \\ieedc-vnasc01\Sites\ [REDACTED]\NLHOF\IntProjects\Consulting\Projects\ Corvidia\ [REDACTED]
Biostatistics\01.Documentation\02.SAPI Corvidia_RESCUE_PROSAP_v2.0_21JUL2020
Author: [REDACTED] Version No: v.2.0
Template No.: [REDACTED] Version Date: 21JUL2020
Effective Date: 01Dec2018 Reference: [REDACTED]

Patients who did not experience definitive clinically meaningful deterioration will be censored at the date of the last available PRO assessment (i.e., date of the last non-missing value). Patients with no baseline assessment or patients with no post-baseline assessments will be censored at the date of randomization.

Document: \\ieedc-vnasc01\Sites\█\NLHOF\IntProjects\Consulting\Projects\Corvidia\█
Biostatistics\01.Documentation\02.SAPI Corvidia_RESCUE_PROSAP_v2.0_21JUL2020
Author: █ Version No: v.2.0
Template No.: █ Reference: █
Effective Date: 01Dec2018 Version Date: 21JUL2020

Copyright © 2018 █ All rights reserved. The contents of this document are confidential and proprietary to █ and its subsidiaries. Unauthorized use, disclosure or reproduction is strictly prohibited.

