1. INTRODUCTION

This document describes the rules and conventions to be used in the presentation and analysis of patient-reported outcomes (PRO) data collected in the COR-001-02 study. It describes the data to be summarized and analyzed, including specifics of the statistical analyses to be performed. It is intended to ensure the credibility of the study PRO results by pre-specifying the statistical approaches for the analysis of PRO data prior to database lock.

This statistical analysis plan (SAP) is based on protocol version amendment 5 dated 23 December 2019.

This plan may be revised during the study to accommodate protocol amendments and/or to make changes to adapt to unexpected issues in study execution and/or data that affect planned analyses. The final plan, if revised, will document all changes and be issued prior to database lock.

Due to the impact of the Coronavirus Disease 2019 (COVID19) pandemic on the RESCUE clinical trial, an immediate discontinuation of dosing was announced on March 18, 2020 to ensure the safety of trial patients. The announcement required the early termination visit to be scheduled as early as possible for ongoing patients followed by their entry into the safety follow-up period.

At the time of discontinuation of the study, approximately 140 patients had completed the 24-week treatment period and more than 120 patients were non-completers of the treatment period.

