5.6. LONGITUDINAL ANALYSIS OF CHANGE FROM BASELINE

Change from baseline to Week 13 and Week 24 in PRO scores will be analyzed using a restricted maximum likelihood (REML)-based repeated measures approach (MMRM – Mixed Model Repeated Measures) (Brown & Prescott, 2006) as described in the clinical SAP.

The MMRM assumes that the missing observations are missing at random (MAR). That is, MMRM assumes that, given the statistical model and given the observed values of the outcome, missingness is independent of the unobserved values. A corollary is that MAR assumes that a subject's missing values can be estimated based on similar subjects who remained in the study. This infers that withdrawals (who may not receive study medication) have similar symptoms to some who continue to be treated. Given the expectation that PRO scores could be lower (poorer quality of life and/or more disease-related symptoms) after discontinuing the study medication, the MAR's assumption of the similarity of withdrawals and those who stay in the study may not be realistic for all subjects. To address the possibility of the data being missing not at random (MNAR) (e.g., non-ignorable missing data), a second analysis may be implemented using a PMM with sequential modelling with multiple imputation using placebo-based imputation (O'Kelly & Ratitch, 2014), depending on the amount of missing data at each visit. Further details on this exploration can be found in Section 5.9.2. The PMM will be used to assess the robustness of the MMRM estimate with regard to missing data when the MAR assumption is replaced by assumptions that are likely to be relatively less favorable to the experimental treatment. Due to the impact of the Coronavirus Disease 2019 (COVID19) pandemic on the RESCUE clinical trial, an immediate discontinuation of dosing was announced on March 18, 2020 to ensure the safety of trial patients. Therefore it is expected that a large number of patients will not have data at Week 24.

Analyses included in the clinical SAP will not be repeated here. The analyses will be performed on the ITT population and for each of the following PRO scores:

- CARES: TSS and other potential subscales resulting from the psychometric analysis
- PROMIS Fatigue: total, symptoms and impact domain from the 13-item set, as well as other potential subscales resulting from the psychometric analysis
- SF-36:

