5.6.2. PMM

Change from baseline in PRO domain and overall scores may be further analyzed using a pattern-mixture model using sequential modelling with multiple imputation as described by O'Kelly (O'Kelly & Ratitch, 2014), depending on exploration of the amount of missing data at post-baseline assessments, as described in Section 5.9.2.

Document: \\ieedc-vnasc01\Sites\[\]\NLHOF\IntProjects\Consulting\Projects\Corvidia\[\]
Biostatistics\01.Documentation\02.SAPI Corvidia_RESCUE_PROSAP_v2.0_21JUL2020
Author: \[\] Version No: v.2.0
Template No.: \[\] Version Date: 21JUL2020
Effective Date: 01Dec2018 Reference: \[\]

The results from this analysis will be used to judge the validity of the MAR assumption. Similar conclusions from MMRM and PMM would suggest that the results are not overly dependent on the assumptions of the primary analysis with regard to the missing data.

The sensitivity analysis will consider dropout reasons while imputing missing values after the discontinuation. Subjects who discontinued due to lack of efficacy or adverse events in the active arms are assumed to have no treatment effect after the discontinuation. These subjects are assumed to copy the profile in the placebo arm, and missing values are imputed based on the distribution estimated from the placebo group under the missing not at random (MNAR), using copy-reference approach. The rest of missing values in the placebo arm and active arms will be imputed using the observed data in their respective group under the MAR assumption. This includes the patients who were early terminated due to the impact of the Coronavirus Disease 2019 (COVID19) pandemic. The multiple imputation model will include factors such as treatment arm, baseline hemoglobin category, and CKD stage, in addition to the data outcomes at each visit.

The following steps will be performed:

Step 1 Intermittent (non-monotone) missing data will be imputed using the MCMC option of SAS PROC MI (using seed=5414).

Step 2 For monotone missing data, the values for each pattern will be imputed via the chained equation method with range restriction, using SAS PROC MI option MONOTONE REG () .

Under step 2, missing values for subjects who discontinued due to lack of efficacy or adverse events will be imputed under MNAR assumption using copy-reference approach, and missing values for subjects who discontinued due to reasons other than lack of efficacy or adverse events will be imputed under the MAR assumption.

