5.7. RESPONDER ANALYSIS

The proportion of patients with improvement, who were stable, or who deteriorated (as defined in section 4.2 using both the primary and the potential sensitivity thresholds if these are suggested by the psychometric analysis) will be summarized at each PRO assessment visit by treatment arms. The denominator in this descriptive analysis will be the number of patients with non-missing data at the particular visit. The analysis will be performed on the ITT population and include only subjects who have an assessment at baseline and at least one post-baseline assessment.

The proportion of patients with definitive deterioration and transient deterioration during the course of the study will be summarized by treatment arms. The denominator in this descriptive analysis will be the number of patients with at least one deterioration during the study.

The analysis will be performed on the ITT population and for each of the following PRO scale scores:

- CARES: TSS and other potential subscales resulting from the psychometric analysis
- PROMIS Fatigue: total, symptoms and impact domain from the 13-item set, as well as other potential subscales resulting from the psychometric analysis

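### The definitive-deterioration rule accepts drop-out for any reason, including the COVID stop, in place of confirmation, and section 5.7 compares arms only among patients who deteriorated

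*SAP*

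**What the plan says.** All references are to PRO SAP v2.0.

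- **Event rule.** Section 4.3.2 defines time to definitive deterioration (TTDD) by a first threshold crossing that is seen at all later time points, "or if the patient dropped out after deterioration, resulting in missing data". Sections 4.2.1 (CARES) and 4.2.2 (PROMIS Fatigue) use the same clause to separate definitive from transient deterioration. None of the three limits it by reason for drop-out.
- **Dating and censoring.** The event is placed at the "Date of assessment when first definitive clinically meaningful deterioration was observed". The remaining patients are censored: "Patients who did not experience definitive clinically meaningful deterioration will be censored at the date of the last available PRO assessment".
- **The stop.** Section 1 reports that "an immediate discontinuation of dosing was announced on March 18, 2020 to ensure the safety of trial patients", and that at that time "approximately 140 patients had completed the 24-week treatment period and more than 120 patients were non-completers of the treatment period". Section 5.6 adds that "it is expected that a large number of patients will not have data at Week 24".
- **Same patients elsewhere.** The optional pattern-mixture model in section 5.6.2 reserves its unfavourable assumption for active-arm patients who left for lack of efficacy or an adverse event. All other missing values are imputed as missing at random: "This includes the patients who were early terminated due to the impact of the Coronavirus Disease 2019 (COVID19) pandemic". Section 5.9.2 lists the pandemic as its own discontinuation group.
- **Use.** Section 5.8, which still labels the endpoint TTCD, compares each dose with placebo by stratified log-rank test and Cox model for the CARES and PROMIS Fatigue scores.
- **Proportions.** For definitive and transient deterioration, section 5.7 states: "The denominator in this descriptive analysis will be the number of patients with at least one deterioration during the study".

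**The concern.** Reading drop-out after a deterioration as lasting worsening is defensible when patients leave because they feel worse. A calendar-driven stop says nothing about how the patient feels. Section 5.6.2 recognises this for the score analyses; the event rule does not. With three post-baseline analysis time points (Weeks 5, 13 and 24), losing one often removes the only chance to see whether a deterioration lasted. If ziltivekimab makes deteriorations shorter rather than rarer, counting unresolved ones as lasting in every arm pulls the hazard ratio towards 1.

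The denominator is a separate defect and does not depend on COVID. Whether a patient deteriorates at all may be affected by treatment. Dividing by deteriorators therefore compares groups that randomisation did not form. An arm that prevents mild, passing deteriorations is left with a higher share of lasting ones.

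**Working it through.** **1. What the documents give.** They state no rate for definitive deterioration. The only relevant count is 120/(140 + 120) = 46% non-completers. This is a reference value only, because the non-completers are not said all to have stopped for COVID or to have deteriorated.

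**2. Who could have a later score.** The CARES Week 24 score averages Days 155 to 168 and is set to missing if more than 7 of the 14 days are missing (4.2.1), so most stopped patients cannot have one. PROMIS Fatigue is collected at the early-termination visit (2.4.6), and such visits are assigned to analysis windows when the scheduled visit is unavailable (4.1.4). Some stopped patients therefore have a later PROMIS score. Section 4.3.2 does not say whether it counts as a later time point.

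**3. Misclassified events.** Take patients whose first deterioration is at Week 13. Let s be the share with no later assessment and r the chance of recovery by Week 24 (both assumed).

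- Definitive share under the rule: s + (1 − s)(1 − r). With full follow-up: 1 − r.
- Share of definitive events that would have reversed: s·r / [s + (1 − s)(1 − r)].

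| s | r = 0.2 | r = 0.4 | r = 0.6 |
|---|---|---|---|
| full follow-up, definitive | 80% | 60% | 40% |
| 0.10: definitive / would have reversed | 82% / 2.4% | 64% / 6.3% | 46% / 13.0% |
| 0.25: definitive / would have reversed | 85% / 5.9% | 70% / 14.3% | 55% / 27.3% |
| 0.46: definitive / would have reversed | 89% / 10.3% | 78% / 23.5% | 68% / 40.8% |

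**4. Dilution.** Suppose treatment acts only on persistence, with recovery 70% on active and 40% on placebo. With full follow-up the risk ratio is 0.30/0.60 = 0.50. Under the rule it is [s + (1 − s)0.30] / [s + (1 − s)0.60]:

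- s = 0.10: 0.370/0.640 = 0.58
- s = 0.25: 0.475/0.700 = 0.68
- s = 0.46: 0.622/0.784 = 0.79

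**5. How much belongs to the stop.** Let each visit cross the threshold with probability 0.2, independently (assumed).

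- Last seen at Week 5: 0.200 definitive, none confirmed.
- Last seen at Week 13: 0.8 × 0.2 + 0.2² = 0.200 definitive, of which 0.040 confirmed, so 80% unconfirmed.
- Completers: 0.8² × 0.2 + 0.8 × 0.2² + 0.2³ = 0.128 + 0.032 + 0.008 = 0.168 definitive, of which 0.040 confirmed. The 0.128 first deteriorate at Week 24, so 0.128/0.168 = 76% are unconfirmed without any stop.

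**6. Total event count.** A three-visit simulation used 20% new deterioration per visit, with 15% last seen at Week 5 and 31% at Week 13. For recovery 0.2 / 0.4 / 0.6 per visit, definitive rates were 0.336 / 0.278 / 0.226 under the rule and 0.383 / 0.297 / 0.223 with full follow-up. Of the rule's events, 9% / 19% / 32% would have reversed.

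**7. Denominator (illustrative counts, 60 per arm).** Active: 10 deteriorate, 6 definitively. Placebo: 30 deteriorate, 15 definitively.

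- Section 5.7 denominator: 6/10 = 60% against 15/30 = 50%. Active looks worse.
- All 60: 6/60 = 10% against 15/60 = 25%. Active looks better.

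**The case against.** The strongest reply is that lack of confirmation is mostly a last-visit property of any such definition with three visits. Step 5 bears this out: 80% unconfirmed for a Week 13 stop against 76% for completers. That stands, and it means one rule must cover both groups.

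A reader might infer three stronger things, which the documents do not support:

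- **That the stop creates events.** A threshold crossing must first be observed, and stopping also removes later chances to deteriorate. In step 6 the total falls in two of three settings.
- **That more than 120 patients are affected.** That is the count of non-completers. Only those whose last available score is a deterioration matter. Even if all 120 had been stopped for COVID, a 20% rate gives 24 patients, about 6 in each of four arms, and early-termination scores would resolve some of these for PROMIS Fatigue.
- **That one arm is favoured.** A calendar-driven stop in a double-blind trial should fall about equally on the arms, so dilution is more likely than a false positive.

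Independent visits (step 5) are also close to a worst case; averaged, correlated scores would persist more often. Missing at random does not mean recovered either: an imputation that uses earlier scores would tend to keep a worsened patient worse. The inconsistency with section 5.6.2 is therefore narrower. There the later course stays uncertain; in 4.3.2 it is fixed as worse.

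On the denominator, section 5.7 labels the summary descriptive and section 5.1 asks for counts, so a reader could recompute. That lowers the stakes, but the printed percentages by arm would still invite the wrong comparison.

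Finally, censoring only COVID-stopped patients at a score that has just worsened would be informative and would treat them differently from completers. This is right, and it rules out that change as a simple replacement.

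**Conclusion.** The point holds in a limited form. The drop-out clause covers every reason, so some COVID-stopped patients become definitive events on one unconfirmed score. This misclassifies some TTDD events and probably dilutes an effect on persistence, more for CARES than for PROMIS Fatigue. Its size rests on s and r, which the documents do not give; the ranges in steps 3 and 4 show only what is possible, and s = 0.46 is not an estimate of the affected share. The denominator defect needs no assumed rate: it conditions on an outcome of treatment and can reverse the direction between arms. Both concern supportive, exploratory analyses with no multiplicity control and leave the hs-CRP primary analysis untouched. The plan should be changed, but the trial's main conclusion does not depend on it.

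**What to change.** 1. **Section 5.7.** Report definitive, transient and no deterioration out of all patients with a baseline and at least one post-baseline score, a restriction that the section already applies to its responder categories. This is a free improvement.
2. **Sections 4.2.1, 4.2.2 and 4.3.2.** State that an early-termination assessment counts as a later time point. Class a deterioration at the last available assessment as unconfirmed, by the same rule for COVID-stopped patients and for completers who first deteriorate at Week 24.
3. **Drop-out clause.** Limit it to discontinuation for adverse event, lack of efficacy or death. Report TTDD twice: with unconfirmed deteriorations as events (the current rule) and with them censored at that assessment.

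The cost is SAP wording and small program edits; no new data are needed, since section 5.9.2 already groups discontinuation reasons this way. The downside is fewer definitive events in the second version and possibly informative censoring there, which is why both versions should be shown.
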